### **11.3. Starting rules**

For the in-clinic days, the subject is to arrive in the clinic around 4 pm. The last meal of the subject, prior to arrival to the clinic should have occurred no later than noon of that day. The subject should not have any insulin bolus after 2:00 pm or ingest any carbohydrate after the lunch, unless it is for treatment of hypoglycemia, i.e. if the subject glucose level is < 70 mg/dL.

The clinical staff may reschedule the subject if the above directions are not followed. If the subject has questions on the day of admission, they should contact the study staff.

#### 11.4. **Stopping rules**

##### 11.4.1. **Criteria for individual subject withdrawal**

The termination of a subject from the study will be documented in the subject source documents and on the CRF. The reason for the termination and possible following effects must be documented. Subjects that have discontinued participation will not be replaced. Should a subject be lost-to-follow-up (LTF), i.e. no return for the on-site 24-hour closed-loop after enrollment, a reasonable effort will be made to contact the subject to determine why the subject failed to return. Any investigator-decided outside intervention will trigger termination of the trial for the subject. If the investigator treats the subject with 16 g of carbohydrates following the recommendation of the HMS, then the trial will not be terminated, this is anticipated and part of the trial. If a trial is terminated, the same subject may be rescheduled and the trial repeated. Rules for terminating a visit for an individual subject are as follows (glucose levels measured by YSI).

- Outside intervention (bolus or carbohydrate treatment) from the investigator that did not follow recommendation from HMS.
- Gross system malfunctions such as:
  - Pump failure
  - Failure of both study sensors
  - System or controller malfunctions that may have an impact on the safety of the subject
- Any correction bolus initiated by the investigator.
- Glucose YSI > 250 mg/dL for more than 2 hours and blood ketones exceed 1.0 mmol/L.
- Subject develops nausea, vomiting, or abdominal pain and blood ketones exceed 1.0 mmol/L.
- Glucose YSI > 350 mg/dL with decreased sensorium with or without emesis.
- Glucose level YSI > 400 mg/dL at any point if the investigator decides to treat with a correction bolus.

- Glucose YSI < 60 mg/dL without having received a HMS warning
- Glucose YSI < 50 mg/dL.
- Severe Hypoglycemia or Hyperglycemia as defined by Table 9-2.
- The subject or physician requests the trial be stopped.
- Failure of YSI equipment.
- Subject withdraws his/her consent.
- Adverse Event which necessitates termination of the study as decided by the investigator, such as DKA.
- Protocol violation: subject is no compliant with procedures, becomes pregnant, violates study entry criteria, or use unacceptable medication.

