YSI + finger stick CONTOUR® EZ	Hypoglycemia: BG<70 mg/dL per YSI Or if AP device (CGM) predicts <70 mg/dL in the following 15 min	Every 15±5 min until YSI >80 mg/dL
YSI + finger stick CONTOUR® EZ	Hyperglycemia: BG>400 mg/dL	Every 15±5 min Until YSI<300 mg/dL
YSI + finger stick CONTOUR® EZ	During exercise	Every 15±5 min and for 1 hour after starting exercise

The AP device includes multiple visual and auditory alarms that are embedded into the APS© software should the system malfunction. The control algorithm also includes intrinsic safety limits that trigger alarms should the patient’s glucose level go too high or too low and which prevents the system from delivering too much insulin.

Should the HMS predict that the glucose level is going to be <70 mg/dL in the next 15 min, the system will alert on the AP device and send a redundant text message to a predefined list of people, which in this study will be only the physician (who will be next to the subject in this study) to notify the subject to eat 16 g of CHO. All warnings issued by the HMS will be documented.

To prevent dehydration secondary to hyperglycemia, the subject will be allowed to consume sugar free beverage during the trial if he/she is thirsty.

Each adverse event will be graded as mild, moderate, or severe as described by [Table 15–1](#) ~~Table 9–4~~. Should there be any Serious Adverse Event or Unanticipated Adverse Device Effect, immediate action for the safety and welfare of the patient will be taken. An investigation will be promptly conducted and reported to the safety

officer of the IRB. All adverse events will be documented as described in section [159](#).

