**Table 10–2: Safety action to take in case of hypoglycemic and hyperglycemic events based on YSI values**

CONDITION	ACTION
Hyperglycemia	
Asymptomatic and serum glucose > 250 mg/dL more than 2 hours Or if subject develops nausea, vomiting or abdominal pain	Test the blood for serum ketones. Check the pump, if not running, change pump. If blood ketones exceed 1.0 mmol/L, the study for this subject will be terminated. If a correction bolus needs to be administered by the study staff, it will be administered with a syringe.
Mild polyuria and polydipsia; serum glucose > 250 mg/dL more than 3 hours	If blood ketones were less than 0.6 mmol/L at 2 hours, recheck blood ketones and check the pump. If pump not running or catheter occluded or leaking, change the pump. If blood ketones > 1.0 mmol/L, then the study for this subject will be terminated. If a correction bolus needs to be administered by the study staff, it will be administered with a syringe.
Glucose level $\geq$ 300 mg/dL for more than 1 hour	Investigator will give a manual correction dose bolus administered with a syringe. The trial will be terminated for this subject.
Emesis, but with a normal sensorium and glucose > 350 mg/dL	The study for this subject will be terminated. Intravenous fluids would be given at a rate of 3,000 cc/M2/day. A manual correction dose of a short acting insulin analog would be given. The insulin infusion set would be changed. The subject would remain in the CRC until serum glucose is < 200 mg/dL. Subject will be monitored for at least 2 hours post treatment by study investigator. In case of reoccurring symptoms the subject shall be transferred to the emergency room by paramedics. If a correction bolus needs to be administered by the study staff, it will be administered with a syringe.
Decreased sensorium (sleepy, difficult to arouse) with or without emesis: glucose > 350 mg/dL	The study will be terminated for this subject. The subject will be transferred to the emergency room for evaluation with electrolytes and pH and monitoring for possible further deterioration of neurological status as a decrease sensorium may be indicative of electrolyte and/or pH abnormalities that could lead to respiratory or cardiac depression if not detected and treated appropriately.
Blood glucose >400 mg/dL	The study is terminated for this subject. The investigator will give a manual (with a syringe) correction bolus.

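### Above 400 mg/dL, Table 10-2 ends the session outright, while Section 11.4.1 ends it only if the investigator decides to give a bolus

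*Combined protocol and SAP*

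**What the plan says.** Table 10-2 in Section 10.4.2.3 is headed "Safety action to take in case of hypoglycemic and hyperglycemic events based on YSI values". Two of its hyperglycaemia rows matter here.

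- The row with the condition "Blood glucose >400 mg/dL" carries no duration and no other qualifier. Its action is "The study is terminated for this subject. The investigator will give a manual (with a syringe) correction bolus".
- The row for glucose at or above 300 mg/dL for more than one hour has the action "Investigator will give a manual correction dose bolus administered with a syringe. The trial will be terminated for this subject".

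Section 11.4.1 introduces its own list with the words "Rules for terminating a visit for an individual subject are as follows (glucose levels measured by YSI". The criterion for the top threshold is "Glucose level YSI > 400 mg/dL at any point if the investigator decides to treat with a correction bolus". No criterion in the list uses 300 mg/dL. The list does include a general one: "Any correction bolus initiated by the investigator".

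On the analysis side, Section 2.2 defines the hyperglycaemic extreme as a YSI value above 400 mg/dL. Table 16-3 reports the percent of time above 400 mg/dL, and the percent of time at or above 300 mg/dL when that lasts more than one hour, from both CGM and YSI. Section 16.1 counts a return to range without physician override as a success.

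**The concern.** Both texts are operative rules for the same event on the same measurement. One ends the session on the reading alone; the other makes the ending depend on a treatment decision. Staff following Section 11.4.1 could continue a session that staff following Table 10-2 would have to stop.

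Three things depend on this.

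- Subject safety: there should be one unambiguous rule at the highest glucose threshold in the protocol.
- The extreme-glucose rows of Table 16-3: termination limits how much time above a threshold can be observed, and also how much total time it is divided by.
- Outcome classification: a subject above 400 mg/dL who is left untreated and later returns to range could count as a success under Section 16.1. Under Table 10-2 the same subject is given a bolus and taken out. Section 11.4.1 also allows a terminated trial to be repeated, so the rule decides who becomes eligible for a second attempt.

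**Working it through.** The plan gives no figure to reproduce here, so the check compares the two texts case by case.

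**Same basis.** Table 10-2 and the list in 11.4.1 both refer to YSI values, so the difference is not one of CGM against YSI.

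**Cases.**

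| Case | Table 10-2 | Section 11.4.1 |
|---|---|---|
| (a) Above 400 mg/dL, bolus given | Ends | Ends |
| (b) Above 400 mg/dL, investigator decides against a bolus | Ends | Not required to end by this criterion |
| (c) At or above 300 mg/dL for more than 1 hour, bolus given | Ends | Ends, through the general bolus criterion |
| (d) At or above 300 mg/dL for more than 1 hour, no bolus given | Ends | No glucose criterion ends it at 300 mg/dL |

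**Does another 11.4.1 criterion close case (b)?** The other high-glucose criteria need more than the reading: above 250 mg/dL for over 2 hours with ketones above 1.0 mmol/L, or above 350 mg/dL with decreased sensorium. The gastrointestinal-symptom criterion also needs ketones above 1.0 mmol/L. Severe hyperglycaemia, in the severity table, is defined by intravenous fluids and altered mental state. An alert subject above 400 mg/dL with low ketones, no need for fluids and no bolus meets none of these. The physician may ask for the trial to be stopped, but that is again a choice and not a requirement. Case (b) is therefore a direct conflict.

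**Cases (c) and (d).** Table 10-2 states the bolus as something that will be given. When it is, 11.4.1 ends the visit too. Case (d) arises only if the bolus is withheld despite Table 10-2, so this is an omission from the list and the lesser half of the point.

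**Effect on the percentages.** Let t1 be the time above a threshold and T1 the session time up to termination. Let t2 and T2 be the corresponding times in the part of the session that is lost.

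- With termination: P = t1 / T1.
- Without termination: P = (t1 + t2) / (T1 + T2).

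Termination raises the percentage if t1/T1 exceeds t2/T2 and lowers it otherwise. The lost part is never observed under the same conditions, and the documents give no basis for t2. Neither the size nor the direction can be calculated.

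**Weight of one subject.** With 12 to 20 subjects planned, one subject is 1/20 = 5% to 1/12 = 8.3% of the sample.

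**Handling in the analysis section.** Section 16 does not say how sessions that end early enter the percent-of-time rows, or what their denominator is.

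**The case against.** The best defence is that the texts agree whenever Table 10-2 is followed. It says a bolus will be given above 400 mg/dL, and a bolus satisfies the condition in 11.4.1. This stands for case (a), but it does not explain the condition. By making termination depend on a decision to treat, 11.4.1 allows for a decision not to treat, and Table 10-2 leaves no room for one.

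The same defence is stronger at 300 mg/dL. A reader might infer that this stop is absent from 11.4.1 altogether. The documents do not support that: a bolus given as Table 10-2 states ends the visit under the general criterion. What remains is that the threshold is not listed in its own right.

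A reader might also take Table 10-1 as a third, conflicting rule, because above 400 mg/dL it sets sampling at "Every 15±5 min Until YSI<300 mg/dL" and so seems to expect the session to go on. That does not follow. The row is not labelled as closed-loop, the table covers the whole CRC stay, and subjects stay after termination until discharge conditions are met. The row fits monitoring after a stop equally well.

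Practical reach may be small. These are secondary measures in an uncontrolled feasibility study, and the summaries of the two earlier IDE studies in Section 3.3 report no value above 400 mg/dL. They are summaries, so they do not rule one out. Finally, 11.4.1 already requires the reason for termination to be recorded, and Section 10.4.2.3 requires interventions to be documented. That stands, and it makes the requested count easy to produce.

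**Conclusion.** The conflict above 400 mg/dL is real and lies in the current text: the same YSI reading may end or continue a session, depending on which section is applied and whether a bolus is chosen. The unlisted 300 mg/dL stop is a lesser point of completeness.

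The conclusion rests on reading the condition in 11.4.1 as allowing a decision not to treat. If the sponsor intended the bolus to be automatic, the conflict is one of wording, but the wording still needs to change.

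A reader might try to size the effect by comparing hours above a threshold as shares of a fixed 24 hours. The documents do not support this, because termination shortens the denominator as well as the numerator. A calculation at 300 mg/dL would also say nothing about the direct conflict, which is at 400 mg/dL. The defensible statement is that the affected rows depend on the stopping rule by an amount and in a direction that cannot be determined from the documents, in a sample where each subject is 5% to 8.3%.

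**What to change.** 1. Reconcile Table 10-2 and Section 11.4.1 to one set of hyperglycaemia stopping conditions, listed in both places or in one place with a cross-reference. This covers whether termination above 400 mg/dL depends on a bolus, and whether the stop at 300 mg/dL for more than one hour is a criterion in its own right. The choice is the sponsor's clinical decision.
2. In Table 16-3, report the number of sessions ended for hyperglycaemia beside the rows for above 400 mg/dL and for at or above 300 mg/dL.
3. State in Table 16-3 that these rows and their denominators are cut off at termination.

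The cost is wording in the two stopping texts, one count drawn from termination reasons already recorded on the CRF, and one sentence in the analysis section. No new data are needed. As Section 3.1 notes, protocol changes go to the FDA and the IRB as the regulations require.

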#### **11.4.2. Criteria for suspending / stopping the study**

In case of a recurring system malfunction or subject safety issue observed across multiple subject visits, the overall study will be suspended (no further subjects at any site) while the problem is diagnosed.

In the event of a UADE, the Sponsor/investigator will evaluate the event and follow-up procedure, including the possible suspension and / or termination of the study.

In the event of a Serious Adverse Event, the Sponsor/investigator will evaluate the root cause of the event and will determine appropriate action, including termination of the study.

The study may resume if the underlying problem can be corrected by a protocol or system modification that will not invalidate the results obtained prior to suspension. Any change to the protocol or the system will need to be approved by the Agency prior to implementation.

The study may also be suspended or terminated if the FDA, IRB or other regulatory authority discontinues the approval of the study protocol or Sansum clinical site participation.

The IRB and FDA will be notified if the study is stopped and permission to resume will be obtained from the IRB and FDA prior to restarting.

## **12.EXPECTED SAMPLE SIZE**

This is a feasibility clinical study; therefore, only approximately 12 to 20 adult subjects will take part to this trial.

## **14. ASSESSMENT OF EFFICACY**

The goal of the study is to evaluate the feasibility of the artificial pancreas device, not to measure its efficacy. However, as described in the statistical section, several outcomes will be measured that may give some indication of the possible efficacy of the device.

## **15. ASSESSEMENT OF SAFETY**

### **15.1. Reporting to regulatory agencies**

The study will be conducted after receiving IDE approval by FDA and Cottage Health System IRB approval.

- All anticipated Adverse Events will be reported in details to both the IRB and FDA with the results of the study within 3 months of the completion of the trial.
- Unanticipated Adverse Device Effects (UADE) will be thoroughly investigated and as required by 21 CFR 812.46, they will be reported to FDA and IRB no later than 10 working days after the sponsor first receives notice of the effect, i.e. 10 days after it occurs since the Sponsor is also the investigator (Sansum).
- The CGM Dexcom® G4® or the insulin pump (OneTouch® Ping®) malfunctions which are not related to the modifications of the interface to include them as components of the AP device or the glucose meter (OneTouch® Ultra® blood glucose meter) will be reported to their respective manufacturers as a complaint per MDR requirements (Animas Corp for the insulin pump and the glucose meter and Dexcom for the G4® CGM).
- Malfunctions related to the interfaces of the CGM or insulin pumps with the APS© platform will also be reported to their respective manufacturers.

## **15.2. Definitions**

### **15.2.1. Adverse Event (AE)**

An Adverse Event (AE) is any untoward medical occurrence in a study subject, irrespective of the relationship between the adverse event and the device(s) under investigation. Anticipated adverse events, such as skin irritation from sensor wear will be recorded in specific sections of the case report forms. However, a severe skin irritation is not anticipated and would be reported on the AE form.

All adverse events may be graded from mild to severe as defined by [Table 15-1 Table 9-1](#).

### **15.2.2. Serious Adverse Event (SAE)**

A Serious Adverse Event (SAE) is any untoward occurrence that is:

- Results in death.
- Life threatening, even if temporary in nature;
- Results in permanent impairment of a body function or permanent damage to a body structure;

- Necessitates medical or surgical intervention to preclude permanent impairment of a body function or permanent damage to a body structure. “Permanent impairment” means irreversible impairment or damage to a body structure or functions, excluding trivial impairment damage.

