No heart rate, no blood pressure	Perform resuscitation. If this occurred all studies would be put on holding pending an investigation of the circumstances leading to this very adverse outcome. Call 911 and transfer the treated subject to emergency room.
Hypoglycemia	
If CGM prediction is <70 mg/dL in	The AP device notifies the physician. The physician treats the

CONDITION	ACTION
the following 15 min	subject with 16 g of oral CHO. The study is not terminated for this subject. This is an anticipated part of the study. YSI frequency will increase to every 15±5 min until YSI >80 mg/dL.
Adrenergic/cholinergic symptoms without neurocognitive changes; YSI <70 mg/dL, but > 60 mg/dL	Subjects would be closely monitored with glucose levels every 15±5 minutes until YSI > 80 mg/dL. The investigator will give CHO if directed by HMS.
Asymptomatic or adrenergic/cholinergic symptoms with serum glucose < 60 mg/dL	If the HMS did not raise hypoglycemic warning, the study will be terminated for the subject. Subject will be treated with oral simple carbohydrates, such as glucose tablets or juice, and glucose by YSI rechecked in 15 minutes, and treatment repeated if glucose remains < 70 mg/dL. With second treatment the insulin infusion will be suspended until glucose is > 70 mg/dL. YSI frequency will continue every 15±5 min until YSI > 80 mg/dL. Subject will be monitored for at least 2 hours post treatment by study investigator. In case of reoccurring symptoms the subject shall be transferred to the emergency room by paramedics.
Moderate neurocognitive change, subject is talking but unable to treat their hypoglycemia without assistance; serum glucose < 50 mg/dL	The study will be terminated for this subject. This is unlikely to occur because treatment would have been given with first glucose < 60 mg/dL and glucose is measured every 15 minutes. Subjects will be treated with oral simple carbohydrates, such as glucose tablets or juice, and serum glucose subsequently rechecked in 15 minutes, and treatment repeated if glucose remains < 70 mg/dL. With second treatment the insulin infusion will be suspended until glucose is > 70 mg/dL. Subject will be monitored for at least 2 hours post treatment by study investigator. In case of reoccurring symptoms the subject shall be transferred to the emergency room by paramedics.

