### 15.2.5. Anticipated adverse events

Each adverse event is graded for its severity from mild to severe as described by [Table 15-1](#)~~Table 9-1~~. This is a measure of intensity only. An adverse event may be severe, but not clinically serious.

**Table 15-1:** Severity of adverse events

Intensity level	Description
Mild	Usually transient, requires no special treatments, and does not interfere with the subject's daily activities
Moderate	Usually causes a low level of inconvenience or concern to the subject and may interfere with daily activities, but is usually ameliorate by simple therapeutic measures.
Severe	Interrupts a subject's usual daily activities and generally requires system drug therapy or other treatment.

Hypoglycemia and hyperglycemia are intrinsic risks and adverse events associated with type 1 diabetes. The level of severity of such events follows a more detailed description as described by [Table 15-2](#)~~Table 9-2~~: it varies from negligible, mild, moderate, severe and very severe. Only hyperglycemia or hypoglycemia that is rated moderate or worse will be documented in a CRF.

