**Table 15–3: Anticipated Adverse Events**

Adverse event	Description
Hypoglycemia	Refer to details in Table 9-2. Only report if moderate or worse.
Hyperglycemia	Refer to details in Table 9-2. Only report if moderate or worse.
Skin irritation	From sensor wear or insulin pump infusion set. Only considered an AE if the irritation is severe or meets definition of SAE
Bruising at the side of insertion of CGM, infusion set, IV	Only considered an AE if bruising is severe or meets definition of SAE.
Infection at the side of insertion of CGM, infusion set, IV	Only considered an AE if infection is severe or meets definition of SAE.
Pain or bleeding at the side of insertion of CGM or infusion set	Only considered an AE if pain or bleeding is severe or meets definition of SAE.
Infection at side of finger stick	Only considered an AE if infection is severe or meets definition of SAE
Glucose sensor break	Glucose sensor rupture leaves a small portion of the sensor under the skin that may cause redness, swelling or pain at the insertion site

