### **15.3. Adverse event reporting and protocol monitoring**

The first concern will be the safety of the subject, and appropriate medical intervention will be made to address any adverse event.

All adverse events will be recorded on the CRF (Appendix 9 of the IDE), including those that may have occurred during the outpatient phase of the trial (the investigator will elicit reports of adverse events from the subject).

In case of a Serious Adverse Event, the study will be put on hold until a thorough investigation is performed and documented to determine the root cause of the event. Based on the results, the Sponsor/investigator will determine appropriate action, including changes to the protocol or termination of the study, and notify the appropriate regulatory authorities if required.

*Intensity:* The intensity of the adverse event will be recorded based on [Table 15–1](#)~~Table 9–1~~. The term severe is a measure of intensity, not clinical severity. A severe AE is not necessarily a serious AE. For example, itching for several days may be rated as severe, but may not be clinically serious.

*Causality:* The study investigator will assess the relationship of any adverse event to be related or unrelated to participation in the protocol by determining if

there is a reasonable possibility that the adverse event may have been caused by the study device or study procedures.

*Outcome:* Adverse events that continue after the participant's discontinuation or completion of the study will be followed until their medical outcome is determined or until no further change in the condition is expected.

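### A first emergency-room transfer or admission judged not to meet the SAE definition starts no study hold and no review with a deadline, and one transfer row falls below the adverse-event recording threshold

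*Combined protocol and SAP*

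**What the plan says.** Section 15.2.2 makes an event serious if it meets any of four criteria: death; "Life threatening, even if temporary in nature"; "Results in permanent impairment of a body function or permanent damage to a body structure"; or a need for medical or surgical intervention to prevent permanent impairment or damage. Neither in-patient hospitalisation nor emergency-room transfer is listed.

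Section 15.3 ties the study-wide hold to that classification: "In case of a Serious Adverse Event, the study will be put on hold until a thorough investigation is performed and documented". It also warns that "A severe AE is not necessarily a serious AE".

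Table 10-2 (Section 10.4.2.3) sets the action for each glycaemic event. Four rows carry the instruction "In case of reoccurring symptoms the subject shall be transferred to the emergency room by paramedics", one of them being "Emesis, but with a normal sensorium and glucose > 350 mg/dL". Other rows order transfer outright.

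On recording, Section 15.2.5 says "Only hyperglycemia or hypoglycemia that is rated moderate or worse will be documented in a CRF", and Table 15-3 repeats for both hypo- and hyperglycaemia: "Only report if moderate or worse". Section 15.3, by contrast, has every adverse event entered on the CRF.

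Three other provisions bear on the point:
- Section 11.4.2 suspends the study for a subject safety issue only when it recurs over several subject visits.
- The Executive Summary promises review of any event in the 24-hour closed loop, with a root cause analysis that separates device from drug and one insulin from the other.
- Section 10.1 has the investigator set the controller's responsiveness factor for each subject in light of the previous subject's results.

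**The concern.** This is a sequential study of 12 to 20 subjects, and it adds a fixed 10U inhaled dose before each meal to a closed-loop system. Its main protection for later subjects is what must happen between one session and the next. If a subject is sent to hospital, one would expect that fact to be recorded as an adverse event and understood before anyone else is dosed.

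The written rules secure this only if the event is classed as an SAE. That judgement rests with a sponsor who is also the investigator (Sections 10.4.2.3 and 15.1). Section 11.4.1 also lets a subject whose session was terminated be rescheduled, so the next exposure could be of the same person. At stake are the timing of the review and the completeness of the adverse-event record. No efficacy result is affected.

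**Working it through.** No sample-size or power arithmetic applies. The check sets Table 10-2 against the seriousness definition (15.2.2), the severity grades (Table 15-2), the recording threshold (15.2.5 and Table 15-3) and the hold rules (15.3 and 11.4.2).

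**Step 1: count the rows.** Table 10-2 has 7 hyperglycaemia rows and 7 hypoglycaemia rows: 7 + 7 = 14. Transfer appears in 3 hyperglycaemia and 5 hypoglycaemia rows: 3 + 5 = 8. A study-wide hold is written into 2 of these, both for absent heart rate and blood pressure. That leaves 8 − 2 = 6 transfer rows without a hold of their own.

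**Step 2: grade those six rows by Table 15-2.**

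| Table 10-2 row (paraphrased) | Transfer | Closest Table 15-2 grade | At or above Moderate? |
|---|---|---|---|
| Vomiting, alert, glucose > 350 mg/dL | if symptoms recur | Moderate by symptoms; Severe by need for intravenous fluids | yes |
| Reduced sensorium, glucose > 350 mg/dL | always | Severe | yes |
| Glucose < 60 mg/dL, no symptoms or adrenergic/cholinergic only | if symptoms recur | Mild | **no** |
| Talking but cannot self-treat, < 50 mg/dL | if symptoms recur | Moderate or Severe | yes |
| Incoherent or refusing treatment, < 50 mg/dL | if symptoms recur | Severe | yes |
| Seizure or loss of consciousness, < 50 mg/dL | always | Severe | yes |

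Exactly 1 of the 6 falls below the recording threshold, and only if the recurring symptoms stay free of neurocognitive change.

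**Step 3: ask what a first transfer triggers.**
- *If any 15.2.2 criterion is judged to be met:* the 15.3 hold applies. The reduced-sensorium, incoherent and seizure rows would probably qualify as life threatening or as needing intervention. The documents do not classify any row, so this is judgement.
- *If none is judged to be met:* 15.3 requires no hold, and a single event cannot meet the several-visits condition in 11.4.2.
- *The unanticipated adverse device effect route* (15.2.3) needs a serious effect or problem that was not anticipated. Table 15-3 lists hypo- and hyperglycaemia as anticipated. Where the route does apply, 11.4.2 requires evaluation, and suspension is only possible.
- *The Executive Summary root cause analysis* covers the event but carries no deadline. Doing it after the last subject would comply.
- *The responsiveness-factor decision* (10.1) does fall between subjects. It tunes the controller and does not touch the fixed inhaled dose, and Section 1.4 requires documentation only of changes to the factor and their reasons.

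**Step 4: exposure.** If the event occurred in the first subject, between 12 − 1 = 11 and 20 − 1 = 19 subjects could follow with no required hold and no dated review. The documents give no transfer rate. The summaries of earlier closed-loop studies in Sections 3.3.3 and 3.3.4 describe no such transfer in 10 + 12 + 12 = 34 subjects, counted study by study. None used inhaled insulin, and part of 3.3.4 was not available for this check.

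**The case against.** The strongest reply is that the plan already looks at these events. The Executive Summary commits to reviewing hypoglycaemia, hyperglycaemia, outside interventions and adverse events, with attribution to device or drug, and Section 16.4.1 repeats the review. Section 10.1 makes glycaemic results from one subject an input to the next. With one site, one principal investigator and a physician always present, nobody would be unaware of a transfer. All of this stands, and a reader who inferred that no review is required at all would be wrong. What is missing is a deadline for that review and a link to the next session.

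Three other readings also go too far:
- *Any event not judged life threatening escapes the hold.* The fourth criterion in 15.2.2 also makes an SAE of an event needing intervention to prevent permanent impairment.
- *FDA and the IRB might hear only about 15 months later* (a study of up to a year, plus three months for the final report). Section 3.1 promises periodic reports to both. Their interval is not stated, so the documents support no figure for the delay.
- *The Mild transfer would go unrecorded.* Section 10.4.2.3 has all actions and interventions documented in the CRF, and 11.4.1 requires the reason for any termination. The event may be missing only as a graded adverse event, because 15.2.5 and Table 15-3 conflict with the general statement in 15.3.

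It is also fair to say that the missing hospitalisation criterion is not the main cause. Table 10-2 speaks of transfer, not admission, so adding that criterion alone would capture no row as worded.

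**Conclusion.** The point holds in a limited form, as a cheap improvement. Six of the eight transfer rows carry no study-wide hold of their own. For any of them, and for an admission that follows, a first event judged to meet none of the four 15.2.2 criteria starts no required hold. Nor does it start a review that must be finished before the next subject is treated or the same subject is rescheduled. One of the six rows can also fall below the adverse-event recording threshold.

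The conclusion rests on reading the recording threshold in 15.2.5 and Table 15-3 as prevailing over the general sentence in 15.3, and on the sponsor/investigator applying 15.2.2 as written. How many of the six rows would be SAEs in practice is a matter of judgement. Frequency is expected to be low: a physician is always present and highly insulin-sensitive subjects are excluded. No probability can be given.

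**What to change.** 1. In Section 15.3, with a matching exception in 15.2.5 and Table 15-3, state that any emergency-room transfer between arrival at and discharge from the research center is recorded as an adverse event, whatever its glucose grade. State also that the root cause analysis promised in the Executive Summary is completed and documented before the next subject is treated or the same subject is rescheduled. The event is an SAE only if it meets 15.2.2. This change does most of the work, and for transfers it removes the conflict between 15.2.5 and 15.3.
2. Add in-patient hospitalisation to the criteria in 15.2.2, so that a transfer ending in admission starts the existing 15.3 hold.

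The cost is a few sentences in 15.2.2, 15.2.5 with Table 15-3, and 15.3. No committee, extra data collection or design change is needed. The downside is a possible short pause for an event that proves minor.
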